#### 5.1.2.2 Assessment of disease progression

Disease progression will be based on the local investigator's tumor assessment.

For patients with measurable disease at baseline, progression will be determined according to the RECIST 1.1 ([R09-0262](#)).

In the absence of measurable disease at baseline, patients with bone lesions, lytic or mixed (lytic + sclerotic), will be allowed to enter the study and the following will be considered disease progression among these patients:

- The appearance of one or more new lytic lesions in bone
- The appearance of one or more new lesions outside of bone
- Unequivocal progression of existing bone lesions

Pathologic fracture, new compression fracture, or complications of bone metastases will not be considered as evidence of disease progression, unless one of the above-mentioned criteria is fulfilled.

Proprietary confidential information.

© 2016 Boehringer Ingelheim International GmbH or one or more of its affiliated companies. All rights reserved.

This document may not - in full or in part - be passed on, reproduced, published or otherwise used without prior written permission.

## 5.2 SAFETY

### 5.2.1 Endpoints of safety

For the phase I part, the primary endpoints are DLT and MTD.

MTD is defined as the highest dose level examined of BI 836845 in combination of everolimus and exemestane, at which no more than 1 out of 6 MTD evaluable patients experienced a dose limiting toxicity during the MTD evaluation period.

The number of MTD evaluable patients per dose level with dose limiting toxicities during the MTD evaluation period will be used for the determination of the maximum tolerated dose.

Safety of BI 836845 when administered together with everolimus and exemestane will be evaluated by intensity and incidence of AEs, graded according to National Cancer Institute (NCI) Common Terminology Criteria for Adverse Events (CTCAE) Version 4.03 dated 14 June 2010 ([R10-4848](#)).

Other assessments of safety include:

- The incidence and intensity of AEs, as well as seriousness and relatedness of adverse events to treatment
- AE leading to dosage reduction or discontinuation
- Change from baseline in laboratory values
- Other safety-related assessments involving ECG parameters and ECOG score will be described with respect to possible changes compared to baseline values. Further details on the analysis of ECG data will be specified in the TSAP.

### 5.2.2 Assessment of adverse events

Safety assessments will consist of monitoring and recording all adverse events (AEs) and serious adverse events (SAEs) and includes periodic physical examinations, measurement of vital signs, assessment of performance status, monitoring of laboratory tests (i.e. haematology, chemistry, coagulation, urine analysis, HBV and HCV) and assessment of cardiac function with periodic ECGs as outlined in the [Flow Chart](#) and [Section 6.2](#).

#### 5.2.2.1 Definitions of adverse events

##### Adverse event

An adverse event (AE) is defined as any untoward medical occurrence, including an exacerbation of a pre-existing condition, in a patient in a clinical investigation who received a pharmaceutical product. The event does not necessarily have to have a causal relationship with this treatment.

Proprietary confidential information.

© 2016 Boehringer Ingelheim International GmbH or one or more of its affiliated companies. All rights reserved.

This document may not - in full or in part - be passed on, reproduced, published or otherwise used without prior written permission.

### Serious adverse event

A serious adverse event (SAE) is defined as any AE which results in death, is immediately life-threatening, results in persistent or significant disability / incapacity, requires or prolongs patient hospitalisation, is a congenital anomaly / birth defect, or is to be deemed serious for any other reason if it is an important medical event when based upon appropriate medical judgement which may jeopardise the patient and may require medical or surgical intervention to prevent one of the other outcomes listed in the above definitions.

The following hospitalizations are not considered to be serious adverse events (SAEs) because there is no “adverse event” (i.e., there is no untoward medical occurrence) associated with the hospitalization:

- Hospitalizations for respite care
- Hospitalization planned prior to informed consent (where the condition requiring the hospitalization has not changed post study drug administration)
- Hospitalization for administration of study drug or PK assessment

### Intensity of adverse event

The intensity of adverse events should be classified and recorded according to the Common Terminology Criteria for Adverse Events (CTCAE) version 4.03 in the eCRF.

### Causal relationship of adverse event

Medical judgement should be used to determine the relationship, considering all relevant factors, including pattern of reaction, temporal relationship, de-challenge or re-challenge, confounding factors such as concomitant medication, concomitant diseases and relevant history. Assessment of causal relationship should be recorded in the case report forms.

Yes: There is a reasonable causal relationship between the investigational product administered and the AE.

No: There is no reasonable causal relationship between the investigational product administered and the AE.

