##### 4.1.1.2 Everolimus (Afinitor®) (investigational product)

Everolimus is a registered commercially available drug and will be provided by the sponsor. However, if the recommended phase II dose of Everolimus is on label, e.g. 10 mg daily, for countries starting the trial with the phase II part, and if local regulation permits, Everolimus will be considered non-investigational product and hence, will be supplied by a pharmacy. For countries starting the trial with the phase I part, Everolimus will be supplied by the sponsor throughout the trial.

Pharmaceutical form: Tablets

Proprietary confidential information.

© 2016 Boehringer Ingelheim International GmbH or one or more of its affiliated companies. All rights reserved.

This document may not - in full or in part - be passed on, reproduced, published or otherwise used without prior written permission.

Source:	[REDACTED]
	(for EU countries)
Unit strength:	2.5 mg and 5 mg
Daily dose:	Phase I part: Starting dose 10 mg continuous daily at Cohort 1a. If necessary, dose deescalation will occur as outlined in Section 4.1.3 until determination of MTD and RP2D. In Phase II part, starting dose will be 10 mg in arm 1 and RP2D in arm 2 as outlined in Section 3.1.1
Duration of use:	Continuous dosing in the absence of disease progression, intolerable AEs or other reason necessitating withdrawal
Route of administration:	Oral (swallowed)
Posology:	Once daily after a meal
Additional information:	Drug should be administered according to the summary of product characteristics for EU or the prescribing information for respective country

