#### 4.1.1.3 Exemestane (Aromasin®) (non-investigational product)

Exemestane is a registered commercially available drug; the generic version of exemestane is now available. Exemestane will not be provided by the sponsor. Instead, it will be provided by a pharmacy.

Pharmaceutical form:	Tablets
Source:	[REDACTED]
	or other companies with therapeutic equivalents
Unit strength:	25 mg
Daily dose	25 mg
Duration of use:	Continuous dosing in the absence of disease progression, intolerable AEs or other reason necessitating withdrawal
Route of administration:	Oral (swallowed)
Posology:	Once daily after a meal
Additional information:	Drug should be administered according to the summary of product characteristics for EU or the prescribing information for respective country. From the start of run-in period through Course 1 Day 8 of

Proprietary confidential information.

© 2016 Boehringer Ingelheim International GmbH or one or more of its affiliated companies. All rights reserved.

This document may not - in full or in part - be passed on, reproduced, published or otherwise used without prior written permission.

phase I part, exemestane from the same manufacture must be used for PK evaluation

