### 5.2.2.2 Adverse event and serious adverse event reporting

All adverse events, serious and non-serious, occurring during the course of the clinical trial i.e., from signing the informed consent onwards through the follow up visit will be collected, documented and reported to the sponsor by the investigator on the appropriate eCRFs / SAE reporting forms. Reporting will be done according to the specific definitions and instructions detailed in the 'Adverse Event Reporting' section of the Investigator Site File.

The terminal half-life of BI 836845 is the longest one compared to that of everolimus and exemestane, the residual effect period (REP) for the study, after elimination of BI 836845, is therefore defined as 42 days in this study. All adverse events from the date of signing of informed consent until the last follow-up visit must be reported. All AEs, including those persisting at the end of follow-up visit, must be followed up until resolved or until sufficiently characterised.

Once the patient completed the follow-up, the investigator does not need to actively monitor patients for adverse events. However, if s/he becomes aware of a SAE(s) that occurred after

Proprietary confidential information.

© 2016 Boehringer Ingelheim International GmbH or one or more of its affiliated companies. All rights reserved.

This document may not - in full or in part - be passed on, reproduced, published or otherwise used without prior written permission.

the patient has completed the follow-up, the event should be reported to the sponsor if considered relevant. Deaths (unless considered drug-related or trial related) will not be reported as SAE when occurring after the follow-up period.

For each adverse event, the investigator will provide the onset date, end date, intensity, treatment required, outcome, seriousness, and action taken with the investigational drug. The investigator will determine the relationship of the investigational drug to all AEs as defined in [Section 5.2.2.1](#).

Table 5.2.2.2: 1 AE/SAE reporting requirements

Time period	Reporting requirements
From signing of informed consent until last follow up visit	Report all AEs and SAEs regardless of relatedness or whether the trial drug was administered. This includes all deaths.

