### 7.3.3 Safety analyses

DLTs will be tabulated for each dose cohort in the Phase I part. The tabulation will be done in two ways:

- DLTs with onset in the first treatment course, and
- All DLTs regardless of treatment course at onset

The definition of DLT and determination of MTD are defined in [Section 4.1.3](#) and [Section 5.2.6](#) respectively.

Adverse events will be graded according to CTCAE, Version 4.03 ([R10-4848](#)). Key safety measures will include:

- The overall incidence and intensity of AEs, as well as seriousness and relatedness of adverse events to treatment
- Events leading to dosage reduction
- Events leading to permanent treatment discontinuation

Other safety-relevant assessments including those involving ECG, and ECOG score, will be described with respect to possible changes compared to baseline values. Further details on the analysis of ECG data will be specified in the statistical analysis plan.

The safety profile will be summarized after the determination of RP2D.

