4.3 CLARIFICATIONS

The following points warrant further clarification:

- If not stated otherwise, date of randomisation will be replaced by first treatment administration of any study medication in the outputs (i.e. including the run-in period) for the Phase Ib part of this trial.
- The terms “progression”, “progressive disease” (PD) and “disease progression” will be used interchangeably within this document.
- The terms “treatment cycle” or “treatment course” will be used interchangeably throughout this document.
- The terms “study medication” and “trial medication” will be used interchangeably throughout this document. These terms may be used for any combination of everolimus, exemestane or xentuzumab, or any of these medications alone. Clarification is given when necessary.
- 

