AEs will be reported with start and end day as calculated from the first day of treatment with study medication. This includes the run-in period for the Phase Ib part.

Incidence and severity of AEs

The incidence of AEs overall (irrespective of relatedness to study medication), related AEs, and SAEs will be reported by severity according to CTCAE grades.

Other significant AEs

Other significant AEs are defined as serious and non-serious AEs that lead to dose reduction or permanent discontinuation of study medication. Their incidence will be reported by severity according to CTCAE grades.

A listing of patients who developed 'other significant' AEs will be provided and a flag for serious and non-serious will be included.

AEs leading to dose reduction or permanent discontinuation will include:

- AEs leading to dose reduction of xentuzumab
- AEs leading to dose reduction of everolimus

Proprietary confidential information © 2018 Boehringer Ingelheim International GmbH or one or more of its affiliated companies

- AEs leading to permanent discontinuation of xentuzumab
- AEs leading to permanent discontinuation of everolimus
- AEs leading to permanent discontinuation of exemestane

AEs leading to death

AEs leading to death during the on-treatment period will be tabulated in a separate table. In this table no CTCAE grades will be shown. For fatal AEs without CTCAE grade 5 or missing grade, the grade will be imputed as CTCAE grade 5. Reported fatal AEs that occurred in the post-treatment period will be listed within the listing containing all post-treatment AEs.

Protocol-specified AESIs

Protocol-specified AESIs are specified in the CTP Section 5.2.2.1. Their incidence will also be reported. DLTs are considered as AESIs only in the Phase Ib part.

Adverse events by user defined AE categories (UDAEC)

UDAEC as defined on project level by the pharmacovigilance working group will be derived and the latest version will be used for the analysis. The categories will be taken as defined in the most recent signed version of the safety Statistical Analysis Plan (SAP) at the time of the DBL. These categories can be found in Table 7.8.1: 1. This document is entitled "8-02-sap-safety-core", which can be found in the Project Data Management and Statistics folder, section 8 (project level), within BIRDS.

Table 7.8.1: 1 Adverse events by user defined AE categories

Term	Group[#]
Hepatic impairment	Drug related hepatic disorders – comprehensive search (SMQ)

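### Adverse-event causality is defined against the investigational product, which some control-arm patients may not receive, and the SAP tabulates drug-related events without defining the term

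*Protocol*

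**What the plan says.** **Rules for the investigator.** Protocol 5.2.2.1, under causal relationship, allows two answers. Yes means: "There is a reasonable causal relationship between the investigational product administered and the AE". No is the mirror image. Section 5.2.2.2 repeats this reference: "The investigator will determine the relationship of the investigational drug to all AEs as defined in" Section 5.2.2.1. It also lists what must be supplied for each event, including "outcome, seriousness, and action taken with the investigational drug".

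**Status of the drugs.** Protocol 4.1.1.3 classes exemestane as non-investigational in its heading. Section 4.1.1.2 is headed as an investigational product. It then says that, for countries starting with Phase II, if the recommended Phase II dose is on label and local regulation permits, "Everolimus will be considered non-investigational product and hence, will be supplied by a pharmacy". Countries that start with Phase I receive everolimus from the sponsor throughout.

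**Analysis.** Protocol 5.2.1 and 7.3.3 summarise events by severity "as well as seriousness and relatedness of adverse events to treatment". SAP 4.3 says of study medication and trial medication: "These terms may be used for any combination of everolimus, exemestane or xentuzumab, or any of these medications alone". SAP 7.8.1 plans tables of drug-related events and serious drug-related events without defining drug-related. It also plans separate counts of events leading to discontinuation of each drug, including "AEs leading to permanent discontinuation of exemestane".

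**The concern.** The definition used for scoring and the definition implied by the analysis do not cover the same drugs, and the mismatch is not symmetric between arms. Arm 2 always contains an investigational product. Arm 1 may contain none.

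Safety of the combination is the secondary objective (Protocol 2.2), and Protocol 7.3 compares the Phase II safety profile between arms. Attribution matters here because Protocol 2.3 raises the possibility that BI 836845 increases the side effects of everolimus, and the trial is open-label. If sites followed the causality rule as written, part of any difference in drug-related events would come from the definition and not from the drugs.

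**Working it through.** No figure in the plan is at issue, so the check sets the texts side by side.

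**Step 1. Which drugs count as investigational.** Inputs: Protocol 4.1.1.1 to 4.1.1.3 for status, 5.2.2.1 and 5.2.2.2 for the rule, SAP 4.3 for the analysis meaning.

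| Everolimus status in the country | Arm | Counted, protocol read literally | Counted, SAP meaning |
|---|---|---|---|
| Investigational | 1 | everolimus (1 of 2 drugs) | 2 of 2 |
| Investigational | 2 | BI 836845, everolimus (2 of 3) | 3 of 3 |
| Non-investigational | 1 | none (0 of 2) | 2 of 2 |
| Non-investigational | 2 | BI 836845 (1 of 3) | 3 of 3 |

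**Step 2. What this does to single events.** On the literal reading, an event due only to exemestane is scored No in both arms everywhere. An event due only to everolimus is scored differently between the two kinds of country, but alike in both arms of one country. The asymmetry between arms comes from the last two rows: Arm 1 has nothing to be judged against and Arm 2 has BI 836845.

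**Step 3. Whether the word is used loosely.** It is not always. Protocol 4.3.2 prescribes pill counts and patient information for investigational everolimus, and local practice for exemestane and non-investigational everolimus. Section 6.1 also treats non-investigational everolimus separately. A site could reasonably carry the same distinction into causality.

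**Step 4. Size.** Let f be the share of patients in countries where everolimus is non-investigational, taken as equal in the two arms. Let q be the proportion of Arm 2 patients there with at least one event judged related to BI 836845. Let r1 and r2 be the literal drug-related rates in Arms 1 and 2 in the other countries.

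- Arm 1 rate = f × 0 + (1 − f) × r1
- Arm 2 rate = f × q + (1 − f) × r2
- Difference = f × q + (1 − f) × (r2 − r1)

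The affected countries therefore contribute a gap of f × q. Neither f nor q is given. Each could lie anywhere from 0 to 100%, so the product has no useful bound.

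Nor is all of f × q necessarily spurious. If d is the difference that those countries would show with all study drugs counted, the distortion is f × (q − d). It equals the whole of f × q when d is 0. It would be negative if BI 836845 raised the rate of events that investigators attribute to everolimus alone by enough to make d exceed q. Overstatement of the excess in Arm 2 is plausible, not certain.

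**The case against.** The strongest reply is that two sentences are being read too hard. Elsewhere the protocol relates events to treatment (5.2.1, 7.3.3) or study drug (the special-interest text in 5.2.2.1, and 5.2.6). Section 8.4.1 names the EU SPC as the listedness reference for everolimus and exemestane, which suggests that events are also assessed against those drugs. SAP 7.8.1 names relationship and action taken with trial medication among the event attributes when it describes CRF data. Section 5.2.2.2 sends sites to the Investigator Site File for instructions. Neither that file nor the eCRF is among the documents, and the SAP follows protocol amendment 3, whereas the protocol at hand is the revision of 30 March 2016. The everolimus condition may apply to few countries or none.

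Much of this stands, and it rules out three stronger readings:

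- A reader might infer that events cannot be scored alike in the two arms. The documents show conflicting definitions, not how sites scored.
- A reader might infer that the exemestane discontinuation table has no collected input. SAP 7.8.1 points the other way. What remains is that 5.2.2.2, as worded, does not ask for that input.
- A reader might size the gap from the 67% in Protocol 4.1.3.2. That is a rate of dose reduction or interruption in another trial, not of drug-related events. Applying the loss to Arm 1 alone also ignores that everolimus-only events in Arm 2 would be scored No under the same reading.

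The reply does not remove the conflict. Sections 5.2.2.1 and 5.2.2.2 are the places that tell investigators how to score each event, and broader wording in the analysis sections cannot change what was collected.

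**Conclusion.** The point holds as an unreconciled definition. The protocol scores causality and action taken against the investigational product or drug, the analysis sections and the SAP mean all study drugs, and drug-related is undefined. The tables of drug-related and serious drug-related events may therefore rest on different bases in the two arms.

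This depends on three conditions that the documents do not settle: that some countries met the everolimus condition, that sites applied the rule literally, and that the eCRF did not override it. The size, about f × q on the literal reading, cannot be calculated.

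Overall adverse-event and SAE incidence is unaffected, because 5.2.2.2 collects events regardless of relatedness. CTCAE grades and PFS are also unaffected. The discontinuation tables are affected only if the eCRF does not already record action taken for each drug. The arm comparison of safety is descriptive, so no formal test is at risk. A wording correction is justified; a claim that safety data were mis-scored is not.

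**What to change.** - In Protocol 5.2.2.1 and 5.2.2.2, refer causality to any study medication received (BI 836845, everolimus or exemestane), whatever its regulatory or supply status, and have action taken recorded for each drug.
- In SAP 7.8.1, define a drug-related event as one related to at least one study medication received.
- Check the eCRF question and the Investigator Site File instructions. If they already cover all study drugs, the change is wording only.
- If the eCRF asked only about the investigational product, state this as a limitation of the drug-related tables and base the arm comparison on all-cause events, which the SAP already tabulates.

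The cost is a few lines in each document and a check of the eCRF, with no new patients, visits or analyses. Recruitment and xentuzumab treatment stopped in October 2016, so the SAP definition and the eCRF check matter most now. Re-asking sites about causality so late in an open-label trial would be laborious and open to recall bias; the limitation statement is the safer course.

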### Worsening of the underlying disease or other pre-existing conditions

Worsening of the underlying disease or of other pre-existing conditions will be recorded as an (S)AE in the eCRF.

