### Exemption to (S)AE Reporting

Disease Progression is a trial endpoint for analysis of efficacy and as such is exempted from reporting as an (S)AE. Progression of the subject's underlying malignancy will be recorded on the appropriate pages of the (e)CRF as part of efficacy data collection only and will not be reported on the SAE Form. It will therefore not be entered in the safety database (ARISg) and

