**Proprietary confidential information.**

**© 2016 Boehringer Ingelheim International GmbH or one or more of its affiliated companies. All rights reserved.**

This document may not - in full or in part - be passed on, reproduced, published or otherwise used without prior written permission.

hence not get expeditiously reported. Death due to disease progression is also to be recorded on the appropriate (e)CRF page and not on the SAE Form.

However, when there is evidence suggesting a causal relationship between the study drug(s) and the progression of the underlying malignancy, the event must be reported as an SAE on the SAE Form and on the (e)CRF.

Examples of exempted events of PD may be:

- Progression of underlying malignancy (Progressive disease [PD]): if PD is clearly consistent with the suspected progression of the underlying malignancy as defined by the respective response criteria.
- Hospitalization/Procedures due solely to the progression of underlying malignancy (PD)
- Clinical symptoms and/or signs of progression (without confirmation by objective criteria e.g. imaging, clinical measurement): if the symptom can exclusively be determined to be due to the progression of the underlying malignancy and does meet the expected pattern of progression for the disease under study.

Exempted events are to be monitored by the study Data Monitoring Committee at the intervals defined in the DMC charter for the phase II part of the trial.

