Observation period (after the patient completed last follow-up and when progression occurred or when new anti-cancer therapy started)	The investigator may report SAE if s/he becomes aware of and considers relevant.  Death should not be reported as a SAE except when it is considered related to trial treatment or trial design (because death is an outcome endpoint and will be followed up separately).

If not stipulated differently in the ISF, the investigator must report the following events via telephone/fax or, if available in the trial, by RDC using the SAE form immediately (within 24 hours) to the sponsor: SAEs and non-serious AEs occurring at the same time as an SAE and/or which are medically related to the SAE(s), and protocol-specified adverse events of special interest.

BI has set up a list of AEs which are defined to be always serious. In order to support the investigator with the identification of these “always serious adverse events”, if a non-serious AE is identified to be serious per BI definition, a query will be raised. The investigator must verify the description and seriousness of the event. If the event description is correct, the item “serious” needs to be ticked and an SAE has to be reported in expedited fashion following the same procedure as above.

The list of these adverse events can be found via the RDC-system.

With receipt of any further information to these events, a follow-up SAE report has to be provided. SAEs and non-serious AEs must include a causal relationship assessment made by the investigator.

Proprietary confidential information.

© 2016 Boehringer Ingelheim International GmbH or one or more of its affiliated companies. All rights reserved.

This document may not - in full or in part - be passed on, reproduced, published or otherwise used without prior written permission.

The SAE form is to be forwarded to the defined unique entry point identified for the BI OPU (country-specific contact details will be provided in the Investigator Site File) or by using the electronic submission process. This immediate report is required irrespective of whether the investigational product has been administered or not and irrespective of causal relationship. It also applies if new information to existing SAEs or protocol-specified adverse events of special interest becomes available.

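### Progression deaths before the last follow-up visit are kept off the SAE Form by Protocol 5.2.2.1 but reportable under Table 5.2.2.2: 1, and the visible SAP text has no rule for them

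*Protocol*

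**What the plan says.** Protocol 5.2.2.1 contains two consecutive paragraphs on this subject. The first is general and covers the cancer and other conditions: "Worsening of the underlying disease or of other pre-existing conditions will be recorded as an (S)AE in the eCRF". The second, under the heading on exemption, says "Disease Progression is a trial endpoint for analysis of efficacy and as such is exempted from reporting as an (S)AE". Progression is to be captured "as part of efficacy data collection only and will not be reported on the SAE Form", and for fatal cases "Death due to disease progression is also to be recorded on the appropriate (e)CRF page and not on the SAE Form". The exemption is lifted "when there is evidence suggesting a causal relationship between the study drug(s) and the progression of the underlying malignancy"; such an event must be reported as an SAE.

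Protocol 5.2.2.2 then sets out reporting by period in Table 5.2.2.2: 1. From consent to the last follow-up visit: "Report all AEs and SAEs regardless of relatedness or whether the trial drug was administered. This includes all deaths". In the observation period that follows: "Death should not be reported as a SAE except when it is considered related to trial treatment or trial design".

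SAP 7.8.1 provides a table of serious adverse events by treatment. It also states "AEs leading to death during the on-treatment period will be tabulated in a separate table", and imputes CTCAE grade 5 for fatal AEs not already graded so. SAP 6.1 counts the residual effect period of 42 days as on-treatment.

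**The concern.** A site handling a progression death before the last follow-up visit has two instructions that cannot both be followed. Section 5.2.2.1 keeps the death off the SAE Form. The table has it reported, with no exception and no reference back to the exemption. If sites resolve this differently, the SAE and fatal-AE tables will mix two conventions, and a reader of the report could not tell which deaths were counted.

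This matters more here than in most settings, because progression or death is the primary endpoint event and safety is compared descriptively between arms (Protocol 7.3). Progression deaths that enter the fatal-AE table bring an efficacy outcome into a safety summary.

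**Working it through.** The plan states no figure on this point to reproduce, so the check is a comparison of texts, followed by a note on scale.

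1. **Instruction for a progression death in 5.2.2.1.** Record it on the relevant eCRF page and do not use the SAE Form, unless there is evidence that study drug caused the progression.

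2. **Instruction in the on-study row of Table 5.2.2.2: 1.** Report all AEs and SAEs, expressly including every death. Cause is not a condition, and no exception is given.

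3. **Could the table mean only recording on an eCRF page?** The surrounding text points the other way. The next row says when a death is not to be reported as an SAE, and limits that to the observation period. The paragraph before the table likewise drops deaths from SAE reporting only once follow-up is over, apart from drug- or trial-related deaths. An exception written for the later period and not for the earlier one implies that deaths in the earlier period are SAE reports.

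4. **Where the instructions do not conflict.** After the last follow-up visit, 5.2.2.1 and 5.2.2.2 agree that an unrelated progression death is not an SAE. Progression suspected to be caused by study drug is reportable under both. Non-fatal progression is covered by the exemption, and the table does not name it. The conflict is confined to progression deaths not suspected to be drug-related, between consent and the last follow-up visit.

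5. **Overlap with the analysis window.** Treatment stops at progression (Protocol 3.1). The first follow-up visit is due 42 to 49 days after permanent discontinuation (Protocol 6.2.3.2). The SAP on-treatment period ends 42 days after treatment. For illustration, suppose a patient stops at progression and dies of her cancer 20 days later. She has not reached the first follow-up visit, so the on-study row applies. Since 20 is less than 42, the death is on-treatment for the SAP. Entered as a fatal AE, it counts in the SAE table, in the fatal-AE table and as grade 5 in the severity tables. Handled under the exemption, it counts in none of them.

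6. **SAP handling.** The visible text of SAP 7.8.1 has no rule to separate or remove progression terms or progression deaths, and the user-defined AE categories in Table 7.8.1: 1 contain no progression category.

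7. **Scale.** Protocol 7.3.1 plans the primary analysis at about 90 progressions or deaths among 150 patients: 90 / 150 = 60%. This is only a very loose ceiling, since it counts non-fatal progression and deaths from any cause, while the conflict concerns progression deaths before the last follow-up visit. The documents give no rate for those. With about 75 patients planned per arm, one patient recorded one way rather than the other changes that arm's percentage by 1 / 75 = 1.3 percentage points.

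**The case against.** The best defence is that the table tells sites to report AEs and SAEs, and Section 5.2.2.1 decides what counts as one. That works for non-fatal progression. It does not work for deaths, because the table names all deaths and Section 5.2.2.2 excludes deaths only after follow-up.

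Several limiting points stand. Section 5.2.2.2 refers sites to the Investigator Site File for detailed reporting instructions, and that file may settle the matter. The SAP follows protocol Amendment 3, dated 15 December 2016, which is not among the documents. SAP 7.8.1 relies on company standards for AE summarisation that are also not available. The window is narrow, because follow-up beyond the first visit ends at progression. The data monitoring committee also reviews exempted events in Phase II.

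A reader might go further in three ways that the documents do not support:

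- **That the worsening paragraph and the exemption flatly contradict each other.** The exemption follows directly, in the same section, and is naturally read as limiting the general rule. The missing cross-reference is untidy but minor.
- **That progression records could swamp the drug-related safety signal.** SAP 7.8.1 tabulates drug-related AEs and serious drug-related AEs separately, and progression judged unrelated would not enter those tables. Tables by preferred term would also show a progression term on its own row.
- **That the between-arm comparison is biased by a known amount.** Randomisation is 1:1 and central, and nothing suggests that sites would apply different conventions by arm. Any rate of early progression death would be an assumption with no anchor in the documents.

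**Conclusion.** The point holds for deaths. In the protocol text available, a progression death not suspected to be drug-related, occurring between consent and the last follow-up visit, falls under two incompatible instructions. The SAE and fatal-AE tables in SAP 7.8.1 inherit the ambiguity. The number of patients affected cannot be derived from the documents; the effect is 1.3 percentage points per patient in an arm of 75.

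The conclusion rests on reading the on-study row as requiring SAE reporting, which its contrast with the observation-period row supports. It also rests on Amendment 3, the Investigator Site File and the company AE standards not having resolved the matter. This is a consistency defect in safety reporting that is cheap to correct. It does not affect the analysis of progression-free survival, which takes deaths from any cause as events regardless of how they are routed for safety.

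**What to change.** **Protocol.** Reconcile the two sections by adding to the on-study row of Table 5.2.2.2: 1: *except deaths due to disease progression exempted in Section 5.2.2.1*. As a minor conforming edit, add *except as exempted below* to the worsening paragraph in 5.2.2.1.

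**SAP 7.8.1.** Show terms for progression of the underlying malignancy on their own line. Give SAE and fatal-AE totals for both arms with and without the exempted progression events. Keep progression events with a suspected causal relationship to study drug in both totals; a blanket exclusion would drop events that 5.2.2.1 says must be reported as SAEs. The total without exempted events does not depend on which instruction a site followed, so this step is useful even for records already collected.

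**Cost.** Two protocol phrases, a short SAP addition and a small amount of extra tabulation. If Amendment 3 or the Investigator Site File already contains the exception, only the SAP addition is needed.
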